10.4.2 Results

Table 2 below provides the probability of group success for each of the groups

Group (Exp N)	Null	Alternative	Two	Half
Breast (20)	0.126	0.924	0.815	0.246
Colorectal (15)	0.059	0.813	0.116	0.743
B-cell Lymphoma (6)	0.063	0.692	0.125	0.180
Melanoma (8)	0.052	0.698	0.517	0.627
ALCL (6)	0.003	0.611	0.045	0.148
Ovarian (15)	0.082	0.839	0.151	0.771
Other (where applicable) (2)	0.011	0.509	0.069	0.294

Entries in bold represent groups where the treatment effect is 0 (e.g. the treatment is ineffective). Thus, entries in bold are type I errors. Entries in italics appear where the treatment is effective, and thus indicate the power of the design.

Generally, type I error is controlled at 0.10 under the null scenario (the borrowing compensates for the multiple interim analyses) and power is an increasing function of the expected sample size (power for Breast, Colorectal, and Ovarian are generally high, particularly in the alternative case). In the alternative scenario there remains decently high probability of success even in the lower enrolling groups. When fewer groups are effective in truth, the scenarios “half” and “two” are harder to discern, however the model still retains around 75-80% power to isolate the highest enrolling groups. In these scenarios identifying the lower enrolling groups becomes more problematic, with power between 50-65%.

Power is reduced and type I error is inflated when the truth is a mixture of effective and ineffective treatment effects across the groups. Generally power again is a function of the sample size.

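### SAP 10.4.2 says type I error is generally controlled at 0.10 under the null because borrowing offsets the interims, but its Table 2 gives 0.126 for Breast, the group most exposed to early-success looks

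*SAP*

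**What the plan says.** SAP 10.1.1 and 10.3.3 declare a group a success if, at the final analysis, the posterior probability that its response rate exceeds the historical rate is above 0.90. Under 10.3.1 and 10.3.2, a group may stop early for futility below 0.10 (at least 10 patients evaluated) or for success above 0.95 (at least 15 evaluated).

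Section 10.4.2 reports the operating characteristics. Its summary sentence reads "Generally, type I error is controlled at 0.10 under the null scenario", and a parenthesis gives the reason: borrowing makes up for the multiple interim looks. A later sentence adds "Power is reduced and type I error is inflated when the truth is a mixture of effective and ineffective treatment effects across the groups".

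The rows of Table 2 give group, expected N, then Null, Alternative, Two and Half. The first row is "Breast (20) 0.126 0.924 0.815 0.246". The two next-largest groups are "Colorectal (15) 0.059 0.813 0.116 0.743" and "Ovarian (15) 0.082 0.839 0.151 0.771". The SAP states that entries for groups with no treatment effect are type I errors, so the whole Null column is type I error.

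**The concern.** The summary sentence and the first entry of the table it summarises do not agree. The sentence also gives a mechanism: borrowing keeps the error at 0.10 despite repeated looks. That mechanism can be tested only in groups large enough to meet the early-success rule, and the group most likely to be that large is the one above 0.10. The inflation that the text admits concerns mixed truths; nothing is said about Breast when no group responds.

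Table 2 is the only simulation in the two documents of a final rule at 0.90. Protocol Appendix Q describes a final threshold of 0.80 and error below 0.20. A reader who wants the false-positive rate of the 0.90 rule will therefore take 0.10 from this sentence, and for the largest planned group the SAP's own table does not support it.

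**Working it through.** **Inputs.** From SAP 10.4.1: 1000 simulated trials per scenario; Poisson accrual with two-year means of Breast 20, Colorectal 15, B-cell lymphoma 6, Melanoma 8, ALCL 6, Ovarian 15, Other 2. From 10.3.2: at least 15 evaluated before early success. From 10.4.2: Table 2.

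**Step 1: the Null column against 0.10.**

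| Group | Null entry | Above 0.10? |
|---|---|---|
| Breast | 0.126 | yes, by 0.026 |
| Colorectal | 0.059 | no |
| B-cell lymphoma | 0.063 | no |
| Melanoma | 0.052 | no |
| ALCL | 0.003 | no |
| Ovarian | 0.082 | no |
| Other | 0.011 | no |

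One of seven exceeds 0.10. The simple mean is 0.396/7 = 0.057. Weighted by assumed accrual (total 72), it is 0.076.

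**Step 2: could 0.126 be simulation noise around 0.10?** The standard error at a true rate of 0.10 is √(0.10 × 0.90/1000) = 0.0095, so z = 0.026/0.0095 = 2.74. The exact tail is P(X ≥ 126 | n = 1000, p = 0.10) = 0.0045. Breast is the largest of seven entries, so a Bonferroni correction is fair: 7 × 0.0045 = 0.032. The exact (Clopper-Pearson) 95% interval for 126/1000 is 0.106 to 0.148, which excludes 0.10.

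**Step 3: which groups test the compensation claim?** Early success needs 15 evaluated patients, so accruing 15 is a necessary condition. P(Poisson ≥ 15) is:

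| Group | Mean | P(N ≥ 15) |
|---|---|---|
| Breast | 20 | 0.895 |
| Colorectal, Ovarian | 15 | 0.534 |
| Melanoma | 8 | 0.017 |
| B-cell lymphoma, ALCL | 6 | 0.001 |
| Other | 2 | < 0.001 |

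Four of the six groups at or below 0.082 almost never qualify for an early-success look, so they say little about whether borrowing offsets such looks.

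**Step 4: mixed truths.** The largest entry for an ineffective group is 0.151 in Two (Ovarian) and 0.246 in Half (Breast). Table 2 prints both; the text gives neither.

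**Step 5: does 0.126 follow from the stated rules?** The design was re-simulated with 20,000 null trials for each reading of the prior on μ. It used Poisson accrual over 104 weeks, a cap of 30, a first look once 30 patients had 16 weeks of follow-up, looks every 13 weeks after that, and the stated thresholds and minimum sizes. Breast came out at 0.097 with 1.82 read as a variance and 0.101 with 1.82 read as an SD. The other six groups fell within 0.02 of Table 2. Breast reached 0.120 to 0.130 only in variants that depart from the stated rules: an early threshold of 0.90, or no minimum group size.

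**The case against.** The strongest defence is the word *generally*. Six of seven entries are at or below 0.082, and the exception is 2.6 points, printed in the first row of a table directly above the sentence. As a description of the column, the qualifier is fair, and that stands. It does not rescue the stated reason, because the exception lies in the group where the interim looks matter most.

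A reader might infer that the 0.246 for Breast in the Half scenario also contradicts the sentence. It does not: the sentence is limited to the null, and the SAP acknowledges inflation in mixed truths. What is missing there is a figure.

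A reader might take the re-simulation as proof that the table entry is wrong, or conversely take 0.126 as proof that the 0.10 sentence is wrong. Neither follows. SAP 10.5 does not say whether 1.82 is a variance or an SD, and the first look is described differently in 10.1.2 (30 patients dosed for 16 weeks or discontinued) and 10.3 (after the first 30 patients). With inputs this loose, a result near 0.10 is a reason to check the entry and no more.

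It would also be too strong to call 0.10 the only protection against a false signal. The 0.95 early-success threshold, the 15-patient minimum, the futility rule and the 0.90 final rule all protect, and no section sets 0.10 as a required limit.

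Finally, current protocol Appendix Q uses other cohorts and control rates (Breast 0.50, against 0.69 in SAP 10.4.1) and a 0.80 final threshold, although the SAP introduction says its Section 10 contains that appendix. That mismatch is a separate matter. It does not remove the disagreement inside SAP 10.4.2.

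**Conclusion.** The point holds as a misstated operating characteristic. Under the null, Table 2 supports at or below 0.082 in six groups and 0.126 in Breast. It does not support the statement that borrowing compensates for the interims to hold 0.10. The excess is modest (0.026; 95% CI for the rate 0.106 to 0.148) in a signal-seeking study, and no decision rule depends on it.

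The conclusion assumes that Table 2 rests on the stated 1000 independent trials. Describing Breast as the largest and most exposed group rests on assumed accrual; the documents give no actual enrolment by tumour type, and the SAP records that the sponsor terminated the study early. Whether the sentence or the table entry needs correcting cannot be settled from the documents.

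**What to change.** Check the Breast null entry against the simulation output under the exact stated interim rules, and re-run the null with more replicates. With 10,000 trials the standard error at 0.10 falls to √(0.10 × 0.90/10,000) = 0.003, enough to separate 0.10 from 0.126. State in the SAP which reading of 1.82 and which timing of the first look were simulated.

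- If 0.126 stands, replace the sentence with: *at or below 0.082 in six of seven groups and 0.126 in Breast under the null; up to 0.25 for ineffective groups in mixed scenarios*. Remove the claim that borrowing fully compensates for the interims.
- If 0.126 does not stand, correct the table.

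The cost is a short re-run and an edit to one sentence or one table entry. The stated error rate may become slightly less favourable. No threshold, minimum size or analysis changes.

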Ceritinib has demonstrated potent antitumor activity in patients with advanced, ALK-rearranged NSCLC ([Shaw et al 2014](#)). As reported in Shaw, et al 2014 a total of 130 patients were treated: 59 patients in the dose-escalation phase and 71 in the expansion phase. Eligible patients had a locally advanced or metastatic cancer harboring genetic alterations in ALK. 122 (94%) patients had NSCLC, among the eight patients with advanced cancers other than NSCLC, two had a response to ceritinib: one patient with anaplastic large-cell lymphoma, and one with inflammatory myofibroblastic tumor.

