10.3.3 Final Analysis

In addition, recall the final analysis will occur when both accrual and follow-up are complete in all groups. If, at the completion of the trial, there is at least 90% probability that the response rate in a group exceeds the historical rate, then the group will be considered a success. Formally:

$$\Pr(\pi_g > R_g) > 0.90.$$

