10.4.1 Assumptions

Accrual - Table 1 shows the assumed two year expected accrual number as well as the assumed control rates for the 7 histologic groups (including “other”). Note these are averages, the actual number of available patients is simulated as a Poisson distribution with the specified mean. Also note that the group cap of 30 applies, and thus if the number of available patients in a group exceeds 30, only the first 30 available patients in that group will be enrolled in the study. Note given the low assumed enrollment rate for “other” (2), there is a high likelihood these subjects will not enroll sufficiently to enter the main analysis.

Dropouts – We assume no dropouts for the purpose of this simulation.

Control Rates – Table 1 also shows the assumed control rates.

Histology	Assumed 2 year accrual	Assumed Control Rate (R_g)
Breast	20	0.69
Colorectal	15	0.26
B-cell Lymphoma	6	0.60
Melanoma	8	0.30
ALCL	6	0.90
Ovarian	15	0.65
Other (where applicable)	2	0.50

Table 1 – Assumed 2 year accrual rates (accrual is simulated as a Poisson process with these means) and assumed control CBR values used in the simulations.

We consider four possible scenarios, or possible “truths” in the simulation. These consisted of a null scenario (where the treatment has no effect for any group), an alternative scenario (where the treatment is effective in all groups), a scenario where the treatment was effective in two of the groups, and a scenario where the treatment was effective in half of the groups.

Treatment Rates - The treatment rates for each scenario are shown in the table below. Values identical to the control are shown in bold, while values greater than the assumed control rate are shown in italics.

	Null	Alternative	Two	Half
Breast	0.69	0.88	0.88	0.69
Colorectal	0.26	0.50	0.26	0.50
B-cell Lymphoma	0.60	0.82	0.60	0.60
Melanoma	0.30	0.55	0.55	0.55
ALCL	0.90	0.97	0.90	0.90
Ovarian	0.65	0.85	0.65	0.85
Other (where applicable)	0.50	0.75	0.50	0.75

Simulation Details – For each scenario we simulated 1000 trials. For each interim within each trial, we ran 50,000 MCMC iterations after a 1,000 MCMC iteration burnin.

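### The ALCL power in SAP Table 2 (0.611) is almost wholly borrowed: with a control CBR of 0.90 and about 6 patients, ALCL's own data can veto a success call but almost never produce one

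*SAP*

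**What the plan says.** SAP 10.1 names ALCL as one of six histologic groups, and SAP 10.1.1 makes a separate decision for each group. Under SAP 10.3.3 a group succeeds if "there is at least 90% probability that the response rate in a group exceeds the historical rate". SAP 6.1 adds a promising category for probabilities between 80% and 90%.

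SAP Table 1, which holds the accrual figures and the "assumed control CBR values used in the simulations", gives ALCL 6 expected patients and a control rate of 0.90. The true ALCL rates under Null, Alternative, Two and Half are "ALCL 0.90 0.97 0.90 0.90". ALCL is therefore effective only where every group is effective.

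SAP Table 2 gives ALCL success probabilities of 0.003, 0.611, 0.045 and 0.148 in those four scenarios. The accompanying text says: "In the alternative scenario there remains decently high probability of success even in the lower enrolling groups". It limits the 0.10 type I error statement to the null scenario and says that type I error rises when effects are mixed.

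**The concern.** The only power shown for ALCL comes from the scenario most favourable to borrowing. With a benchmark of 0.90 and about 6 patients, ALCL's own data carry little information about exceeding the benchmark, so the 0.611 could come mainly from the other tumors. No scenario has ALCL alone effective or ALCL alone ineffective, and these are the two that would show it.

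The study seeks signals by tumor type, and ALCL has prior activity: protocol 1.2.1 reports that, among eight patients with cancers other than NSCLC, "two had a response to ceritinib: one patient with anaplastic large-cell lymphoma, and one with inflammatory myofibroblastic tumor". A reader of Table 2 would expect an ALCL effect to be found about 61% of the time, and would read a success call as evidence about ALCL. If the figure is borrowed, a signal confined to ALCL would be missed, and a success call could reflect activity elsewhere.

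**Working it through.** **Inputs (SAP 10.1.2, 10.3, 10.4.1, 10.5).**
- Expected accrual 20/15/6/8/6/15/2 and control rates 0.69/0.26/0.60/0.30/0.90/0.65/0.50, in Table 1 order. On accrual: "the actual number of available patients is simulated as a Poisson distribution with the specified mean".
- "We assume no dropouts for the purpose of this simulation".
- Dirichlet process mixture with concentration 2; within a cluster θ ~ N(μ, τ²), τ² ~ IG(3, 0.5), μ ~ N(0, 1.82). The SAP does not say whether 1.82 is an SD or a variance, so both were run.
- Futility below 0.10 (n ≥ 10), early success above 0.95 (n ≥ 15), final success above 0.90, cap 30, Other included if n ≥ 3.

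The posterior was computed by summing over all partitions of the groups with numerical integration in place of MCMC, mostly with 2,000 to 6,000 trials per scenario.

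**Step 1. Reproduce the ALCL row.**

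| | Null | Alternative | Two | Half |
|---|---|---|---|---|
| SAP Table 2 | 0.003 | 0.611 | 0.045 | 0.148 |
| SD 1.82, first look at 30 enrolled | 0.002 | 0.617 | 0.040 | 0.132 |
| SD 1.82, first look 16 weeks later | 0.001 | 0.593 | 0.047 | 0.118 |
| Variance 1.82 | 0.001 | 0.476 | 0.025 | 0.069 |

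SAP 10.4.1 states "For each scenario we simulated 1000 trials", so the Monte Carlo error of 0.611 is ±1.96·√(0.611·0.389/1000) ≈ ±0.03. The SD reading reproduces the row to within about 3 points; the variance reading does not. Some other cells, mainly Breast and Melanoma in Half and the Other row, differ by 3 to 18 points, probably through interim timing and how Other is counted.

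**Step 2. What ALCL's own data can do.** Posterior Pr(π > 0.90) with SD 1.82:

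| ALCL result | Others null-like | ALCL alone | Others Alternative-like |
|---|---|---|---|
| 6/6 | about 0.71 | 0.815 | 0.94 |
| 5/6 | 0.43 | not run | 0.73 |

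Null-like means Breast 14/20, Colorectal 4/15, B-cell 4/6, Melanoma 2/8, Ovarian 10/15. Alternative-like means 18/20, 8/15, 5/6, 4/8, 13/15.

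Analysed alone, ALCL needs 11/11 to pass 0.90 (14/14 if 1.82 is a variance). With mean accrual 6, P(N ≥ 11) = 0.043 and P(N ≥ 14) = 0.004. With null-like others it needs 20/20.

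**Step 3. The veto.** With Poisson(6) accrual, P(no ALCL failure) = exp(−6(1 − π)):
- π = 0.97: exp(−0.18) = 0.835
- π = 0.90: exp(−0.60) = 0.549

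In the simulations almost every ALCL success came from a failure-free result. With one failure, the success probability was 0.001 or less. These two values are therefore practical ceilings on ALCL power and false success.

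**Step 4. The two scenarios not in Table 2** (threshold 0.90).

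| Scenario | SD 1.82 | Variance 1.82 |
|---|---|---|
| ALCL 0.97, all others at control | 0.0045-0.008 | 0.001-0.004 |
| ALCL near 1.00, all others at control | 0.010 | not run |
| ALCL 0.90, all others at Alternative | 0.35-0.39 | 0.26-0.29 |

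The ranges cover interim timing and run size. One run shows the mechanism. With all others effective and ALCL ineffective, 0.556 of trials were failure-free and 0.661 of those succeeded: 0.556 × 0.661 = 0.368. With ALCL alone effective, 0.836 were failure-free but only 0.005 of those succeeded.

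For an identical 6/6 result, ALCL was declared a success in 0-0.1% of trials when the others were null and in 80-85% when they responded.

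**The case against.** Borrowing is the declared purpose of the model (SAP 10.2), and the study is exploratory. Table 2 does not conceal the dependence: across Null, Two and Half the ALCL truth stays at 0.90 while its success probability rises from 0.003 to 0.148, about 50-fold, and the text admits inflation under mixed effects. The sentence on lower enrolling groups is confined to the Alternative scenario and is not false for 0.611. All of this stands. What remains is that the two most informative scenarios were not run, and that the text does not say what the 0.611 depends on.

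Three stronger readings are tempting but not supported:
- That the other cohorts alone set the ALCL verdict. ALCL's own data hold a veto: 5/6 gives 0.73 even with Alternative-like others. With all others effective, success is 0.61 if ALCL works and 0.35-0.39 if it does not, so the rule does respond to ALCL.
- That false success is about 1 in 3 whenever other cohorts respond. That needs all of them at their Alternative rates. Where only some respond, the SAP's own figures are 0.045 and 0.148.
- That a perfect 6/6 cannot even be promising. Alone it gives 0.815, inside the promising band; it falls below 0.80 with null-like others, or alone at 0.77 under the variance reading.

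The ALCL inputs may also not be current. Amendment 1 says the control rates should be changed to fit the population enrolled. Protocol Appendix Q lists no ALCL rate and uses a final threshold of 0.80, whereas SAP Section 10 and protocol 10.4 use 0.90, although the SAP introduction says Appendix Q is reproduced in its Section 10. This is a fair limit on the figures.

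**Conclusion.** The concern holds in this form: under SAP Section 10, other cohorts' responses are in practice necessary for an ALCL success but not sufficient, and a failure-free ALCL result is also needed. The printed power of 0.611 falls to about 0.5-1% when ALCL is the only effective cohort. False success reaches about 0.35-0.39 when ALCL is the only ineffective one, more than twice the largest printed value of 0.148. An ALCL success call therefore only weakly separates an effective drug from an ineffective one when the other tumors respond.

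This rests on R = 0.90, mean accrual 6, no dropouts, the 0.90 threshold and 1.82 read as an SD. Under the variance reading false success is 0.26-0.29, and the conclusion is unchanged. At Appendix Q's 0.80 threshold, with R = 0.90 kept and a final look only, the figures become about 15% (ALCL only) and 58% (false success). The size therefore depends on which rule governs.

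The documents do not support going further and calling the ALCL decision invalid.

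**What to change.** 1. Reconcile the final threshold and the control rates between SAP Section 10 (0.90, with an ALCL rate of 0.90) and protocol Appendix Q (0.80, no ALCL rate). State whether 1.82 is an SD or a variance.
2. Under the reconciled rule, add two scenarios to SAP Table 2: ALCL only, and all except ALCL.
3. Qualify the sentence on lower enrolling groups in SAP 10.4.2 by stating that the ALCL figure depends on borrowing.
4. State in SAP 6.1 that any ALCL success or promising call will be reported as dependent on the other cohorts, beside ALCL's own x/n for CBR and ORR with exact 95% CI at whatever n is reached. This waives the 10-subject floor in SAP 6.2 and protocol 10.5.1 for ALCL. The interval will be wide: for 6/6 the lower limit is 0.025^(1/6) = 0.54.

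Dropping the ALCL CBR decision altogether is optional. The SAP records that the study has already been terminated, so removal now would be post hoc, and ORR at about 6 patients has no benchmark in the plan.

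The cost is two more simulation runs, a few sentences, and a Table 2 that looks less favourable.

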10.5 Modeling Details

Recall at the first stage the groups are clustered according to a Dirichlet Process Mixture Model.

The number of clusters is not assumed to be known in advance but will instead be inferred from the data using Dirichlet Process Mixtures (DPM). The DPM looks across all the possible clusterings of the groups and assigns a probability to each based on the data. The prior distribution in a DPM is governed by a parameter α . When α is small, the prior favors large clusters. As α tends to zero, the prior tends to place all its mass on a single cluster containing all the groups. As α increases, the prior places more mass on clusterings with a large number of clusters. As α becomes very large, the prior places all of its mass on having a separate cluster for each group (that is, no borrowing across groups). Thus, by specifying extreme values of the prior one could force the groups into one cluster or force the groups to be analyzed in separate clusters. Here we choose a moderate version of $\alpha=2$ (common values might be anywhere between 0.5 and 5) and allow the data more control over the clustering.

The details of the prior are as follows. Let z_g represent the cluster to which group g belongs. Then $z_g \sim \text{Categorical}(\mathbf{p})$, where \mathbf{p} is the vector such that p_k is the probability that a group belongs to cluster k and $\sum_{k=1}^{\infty} p_k = 1$. We construct \mathbf{p} using a stick-breaking process:

$$p_k = \beta_k \prod_{i=1}^{k-1} (1 - \beta_i)$$

and

$$\beta_k \sim \text{Beta}(1, \alpha).$$

A large value of α thus removes a very small amount of probability for p , resulting in many clusters, while a small value of α tends to produce probabilities near 1 for the first cluster.

Conditional on the clustering, we fit a hierarchical model which has an across groups distribution

$$\theta_g \sim N(\mu, \tau^2)$$

As discussed above, this across groups distribution states that within a cluster we expect to see some variation in the parameters, with that variation governed by τ . When τ is small, there is minimal variation across groups within a cluster, and thus within the cluster the model would approach pooling. In contrast, when τ is large we expect large amount of across group variation, and thus even though the groups are in the same cluster the θ_g values may be quite different. Apriori we have no way of knowing τ , so we estimate it using the data combined with the prior distributions

$$\mu \sim N(0, 1.82)$$

and

$$\tau^2 \sim IG(3, 0.5),$$

where $IG(\alpha, \beta)$ is the inverse gamma distribution defined by:

$$f(x|\alpha, \beta) = \frac{\beta^\alpha e^{-\beta/x}}{x^{\alpha+1} \Gamma(\alpha)}.$$

When the entire model is implemented (via Markov Chain Monte Carlo) we consider the full joint distribution of the clustering combined with the hierarchical model parameters. We average over the entire range of the uncertainty in the parameters to produce the posterior distribution for each group parameter θ_g , which is then used to drive the decisions in the model.

11 References

